ART. In 266 ART-naïve children from the PAANTHER 01 study, 212 (79.7%) were initiated on ART at a median time of 24 (IQR: 14 - 41) days. Children treated for TB started ART later than children not treated for TB [30.5 (IQR 17.0 - 41.5) vs. 14.0 (IQR 11.0 - 32.5) days; p<0.0001]. 26 and 24 deaths occurred before and after ART initiation, respectively. Initiation of ART during follow-up, whatever the timing, was associated with a strong decrease in mortality (p<0.00001). In the multivariate analysis, ART was associated with an estimated 91.6% reduction in the risk of death over the first month of the study [hazard ratio (HR) 0.084; 95%CI 0.010-0.670]. Reduction in time to TB treatment initiation and subsequent earlier ART introduction should lead to improved survival, especially in this population at very high risk of death.

Children not initiated on TB treatment as per the PAANTHER algorithm could immediately benefit from ART initiation. Isoniazid Preventive Therapy (IPT) will be proposed to prevent incident TB but time to initiation of IPT may depend on the level of immune suppression. In children recently initiated on ART, the possible occurrence of unmasking immune reconstitution inflammatory syndrome (IRIS) will be managed cautiously with adjunctive steroids if needed. In those presenting with TB in a context of ART failure, ART should be modified quickly for improved immunologic and clinical outcomes.

Given the high sensitivity of the algorithm, it is expected that only a small proportion of children with TB will be missed in the group not initiated on treatment. Therefore, since true TB cases not recognized by the algorithm (false negative cases) are expected to be a low proportion, the risk of unmasking TB IRIS under ART due to missed TB case at ART initiation is expected to be low.

Given the relatively low specificity of the algorithm, it is expected that there will be a significant proportion of children later classified as unlikely TB in those initiated on TB treatment as per the PAANTHER TB treatment decision algorithm. Despite the better safety profile of first-line TB treatment (very low risk) and ART in children compared to adults, some children with unlikely TB could therefore be exposed to unnecessary cumulative drug toxicity, drug-drug interactions requiring additional safety monitoring, and high pill burden, eventually hampering adherence to ART and TB treatment.

Validation of the PAANTHER TB-treatment decision algorithm

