3. STUDY ENDPOINTS

- 3.1. Primary study endpoint
 - 1. Proportion of missed TB cases (false negative cases) in children not initiated on treatment as per the PAANTHER TB treatment decision algorithm

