An Endpoint Review Committee will be set up at the national level for the purpose of case review and validation of TB diagnosis. The national Endpoint Review Committee will review and validate all new TB cases in children initially non-treated for TB, using the updated Clinical Case Definitions for Classification of Intrathoracic Tuberculosis in Children (see Table 2). The Endpoint Review Committee will also validate differential clinical and other diagnoses on opportunistic infections and adverse events. All reviews will be performed following Standard Operating Procedures (SOPs) specifically developed for the study.

Additionally, at the international level, an Expert Committee will be set up for the purpose of clinical validation of TB diagnosis, including identification of children with unlikely TB in those initiated on treatment as per the PAANTHER TB treatment decision algorithm. The International Expert Committee will validate final TB diagnosis and will determine, based on timing, clinical features, and any other relevant information whether missed TB cases are false negatives, potential TB unmasking IRIS or new TB infections. The use of the updated Clinical Case Definitions for Classification of Intrathoracic Tuberculosis in Children will not be possible as treatment decision is not clinician based but algorithm-guided. The Expert Committee will also review part of all cases reviewed at country level to ensure homogeneity of classification across countries (See figure 2).

The Clinical Case Definitions for Classification of Intrathoracic Tuberculosis in Children were initially developed for children with suspected TB and may not be fully relevant for children with HIV infection [59]. They may be revised by the Scientific Advisory Board (SAB) based on current state of the art on time of final case review.

For the purpose of reference diagnosis and case definition, CXRs will be read by 2 independent experts experienced in reviewing CXRs in children, blinded to all of the clinical information and to each other's interpretation. In case of disagreement, advice from a third expert will be sought. For routine care, CXR will be read by the site clinician.

 Table 2. Updated Clinical Case Definitions for Classification of Intrathoracic Tuberculosis in

 Children (adapted from Graham et al, 2015 [59])

| Case definition | Refined criteria | | | |
|-----------------------------|---|--|--|--|

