4.2. Methodology

The PAANTHER algorithm was initially developed in two countries from South-East Asia (Cambodia, Vietnam) and two West African countries (Burkina Faso, Cameroon). To assess the algorithm's performance outside of its development settings, the study will be purposefully implemented in 4 different countries across Africa where TB incidence, HIV prevalence, patient mix and healthcare practices are likely to vary: Côte d'Ivoire, Uganda, Mozambique, and Zambia (Table 1).

The PAANTHER TB treatment decision algorithm will be used for a TB treatment decision by site clinicians in all children enrolled in the study. Validation of the algorithm will be performed by evaluating the proportion of missed TB cases in children not initiated on treatment as per the PAANTHER TB treatment decision algorithm. The safety of this strategy will be carefully assessed through review of safety reports every 4 to 6 months during study conduct by the IDMC.

Occurrence of algorithm failures in terms of missed TB cases (TB cases subsequently detected among untreated cases, i.e. false negatives) and cases with unlikely TB among those initiated on TB treatment as per the algorithm (cases not secondarily validated as confirmed or unconfirmed TB cases by the Expert Committee, i.e. false positives) will enable to estimate the negative and positive predictive values of the algorithm.

A centralized international Expert Committee will clinically review and validate TB diagnosis in children. This will enable assessment of the added value of new markers (MLR and CRP) and, if need be, to propose a new version of the score based on an optimised predicted probability.

• Study adaptation to the Covid-19 pandemic

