4.3. Sample size

Data obtained from the PAANTHER study showed that the TB prevalence was 57.3% in HIVinfected children with presumptive TB as defined per standard algorithm entry criteria, with a proportion of 39.3% of children being on ART. We expect a higher proportion of children on ART in this new study, reaching 50%, and a resulting lower prevalence of TB, around 50%, based on improved accesss to HIV care in our study settings.

With an algorithm sensitivity and specificity of 89% and 61%, respectively, the proportion of missed TB cases among children not started on treatment based on the PAANTHER algorithm (assessed by the TB incident cases in the 6 months period after applying the algorithm) is estimated to 15%, which corresponds to a negative predictive value (NPV) of 85%. For sample size calculations, we used this expected NPV of 85% and an unacceptable NPV of 75% (minimal acceptable 95% lower confidence interval limit), a one-sided test of level 5% and a probability β =5%, which results in a sample of 176 children not-initiated on treatment as per

the PAANTHER TB treatment decision algorithm and a total sample of 550 children, taking into account an expected 10% of missing data [63].

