11.2. Description of the statistical analysis plan

11.2.1. Analysis of the primary endpoint and algorithm validation

We will evaluate the proportion of missed TB cases in HIV-infected children with presumptive TB not initiated on treatment as per the PAANTHER TB treatment decision algorithm (i.e. false negative cases). We will then estimate the NPV (NPV=1-proportion of false negative) of the PAANTHER TB treatment decision algorithm and its 95% confidence interval. The NPV will be compared to the 75% minimal acceptable lower confidence interval limit.

The algorithm will be considered validated if its NPV remains significantly higher than 75% if the prevalence is at 50%, corresponding to a sensitivity significantly higher than 80%. If a lower diagnostic accuracy is found, we will update the existing prediction model and adjust or recalibrate it to the validation sample.

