13.3. Independent Data Monitoring Committee

The IDMC is a consultative board for the SAB and the sponsor. It monitors the main safety and outcome measures and the overall conduct of the study, with the aim of protecting the safety and the interests of the study participants. Its members will provide general advice on the progress of the study, including the rate of inclusions, quality of follow-up, overall rate of AEs, changes in patients' biological markers, overall incidence of primary outcome (i.e. missed TB cases), and the number of subjects needed.

It will review regular 4 to 6-monthly reports on the primary endpoint, i.e. incident TB cases in children not initiated on TB treatment as per the PAANTHER TB treatment decision algorithm. These reports will include a brief clinical description as well as individual outcomes for each child. The report will include global morbidity and mortality data in this group. They will oversee global safety and provide advice on the continuation of the study or adaptation of the protocol in case of safety concerns in this group of children.

During the study, the IDMC may be asked to deliberate on questions relative to the scientific and ethical integrity of the study, at the request of the SAB, the coordinating investigators, the international coordinating CTU or other participants in the study. The IDMC will provide a formal written opinion report to the SAB and the sponsor after each IDMC meeting.

IDMC members will be selected in collaboration between the coordinating investigators and the sponsor before to the start of the study. All IDMC members must be free from any direct involvement in the study. Any competing interests, both real and potential, must be declared. The list of members will be provided to relevant Ethics Committees when the IDMC is constituted, prior to launching the study. The IDMC will meet before the first inclusion, and every 4 to 6 months until the end of the study. The sponsor, the SAB or the IDMC may request to increase the frequency of these meetings.

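### Whether a missed TB case labelled unmasking IRIS counts as a false negative is stated in two ways, and the reading that leaves it out biases the primary NPV upward

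*Protocol*

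**What the plan says.** - **Primary endpoint (Section 3.1).** "Proportion of missed TB cases (false negative cases) in children not initiated on treatment as per the PAANTHER TB treatment decision algorithm". Missed case and false negative are treated as the same thing.
- **Adjudication (Section 3.3).** The international Expert Committee validates the final TB diagnosis and decides "whether missed TB cases are false negatives, potential TB unmasking IRIS or new TB infections". The basis is timing, clinical features and any other relevant information. No criteria or time window are given, and the section does not say how the second and third classes enter the endpoint.
- **NPV (Section 11.2.1).** "NPV=1-proportion of false negative", followed by "The NPV will be compared to the 75% minimal acceptable lower confidence interval limit".
- **Origin of unmasking IRIS (Introduction, expected benefits and risks).** Because few false negatives are expected, "the risk of unmasking TB IRIS under ART due to missed TB case at ART initiation is expected to be low".
- **What is counted elsewhere.** Section 4.2 speaks of "missed TB cases (TB cases subsequently detected among untreated cases, i.e. false negatives". Section 4.3 sizes the study on missed cases "assessed by the TB incident cases in the 6 months period after applying the algorithm". Section 13.3 gives the IDMC, as the primary endpoint, "incident TB cases in children not initiated on TB treatment as per the PAANTHER TB treatment decision algorithm". None of the three makes an exception for IRIS.

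**The concern.** The NPV is built on the term false negative. Section 3.3 makes false negative one of three classes into which a missed case can fall. If the Section 11.2.1 formula is applied to that class alone, a child whose TB is labelled unmasking IRIS leaves the numerator. Yet the Introduction treats unmasking IRIS as a consequence of TB that was present and not recognised, which is an algorithm miss.

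The effect runs in one direction: taking true misses out of the count can only raise the NPV. The label is also assigned after TB has been detected, without stated criteria. At stake is the decision the study exists to make, namely whether it is safe to withhold TB treatment on a negative algorithm result. In addition, the IDMC could be following a different numerator from the one in the final analysis.

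**Working it through.** **Inputs from the protocol.** Section 4.3: expected NPV 85%, unacceptable NPV 75%, one-sided 5% test, β = 5%, sensitivity 89%, specificity 61%, prevalence 50%, 10% missing data. Section 11.2.1: limit of 75%.

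**Input assumed.** The share *s* of true misses labelled unmasking IRIS. The protocol gives none, so a range is shown.

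**Step 1: reproduce the plan's figures.**
- Algorithm-negative fraction = 0.5 × 0.11 + 0.5 × 0.61 = 0.36.
- Missed proportion = 0.055 / 0.36 = 15.3%, so NPV = 84.7% (stated: 15% and 85%).
- Exact one-sample binomial test of 75% against 85%: the smallest n with α ≤ 5% and power ≥ 95% is 176, as stated. Validation requires at least 142 of 176 without missed TB, so at most 34 misses. Attained α is 4.62% and power 95.25%.
- Total = 176 / 0.36 / 0.9 = 543, against 550 stated.

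The sample size is sound. It rests on all incident TB over 6 months.

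**Step 2: leave IRIS-labelled cases out.** Let q be the true missed proportion.
- Child kept in the denominator as a non-miss: apparent NPV = 1 − q(1 − s).
- Child dropped from the denominator: apparent NPV = (1 − q) / (1 − qs).

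For q = 0.25 (true NPV at the unacceptable 75%) and s = 20%: kept, 1 − 0.25 × 0.8 = 80.0%; dropped, 0.75 / 0.95 = 78.9%.

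**Step 3: probability of declaring the algorithm validated at a true NPV of 75%.** When the child is kept, this is the probability of at least 142 in 176 at the apparent NPV. When the child is dropped, it is averaged over the reduced denominator, applying the exact 5% rule at each size.

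| Share *s* labelled IRIS | Apparent NPV, kept | P(validated), kept | Apparent NPV, dropped | P(validated), dropped |
|---|---|---|---|---|
| 0% | 75.0% | 4.6% | 75.0% | 4.6% |
| 10% | 77.5% | 18% | 76.9% | 12% |
| 20% | 80.0% | 45% | 78.9% | 29% |
| 30% | 82.5% | 77% | 81.1% | 54% |
| 50% | 87.5% | 99.6% | 85.7% | 95% |

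**Step 4: a single data set near the boundary.** Suppose 40 of 176 are missed: 136/176 = 77.3%, exact one-sided 95% lower bound 71.5%, not validated. Relabel 6 of the 40.
- Kept as non-misses: 142/176 = 80.7%, lower bound 75.1%, validated.
- Dropped: 136/170 = 80.0%, lower bound 74.3%, not validated. Under this handling 8 of the 40 must be relabelled (136/168 = 81.0%, lower bound 75.3%).
- Kept, but with a two-sided 95% interval: 142/176 has lower limit 74.1%, not validated. At most 32 misses would pass.

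The direction is the same in every case. Whether one data set crosses the limit depends on the handling.

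**The case against.** A reader might infer that the protocol removes unmasking IRIS from the endpoint and that the NPV is therefore inflated. The documents do not go that far. No section says such cases are excluded. In Section 3.3 the subject of all three classes is missed TB cases, so an IRIS-labelled case is still called missed, and the primary endpoint is the proportion of missed cases. Read with Sections 4.2, 4.3 and 13.3, the split could be purely descriptive. This stands, and it makes the inflation conditional. It does not remove the conflict, because false negative is both the gloss for the whole endpoint and one class of three, and the NPV formula uses that term.

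A reader might also take the 40-to-34 example as showing that a small amount of relabelling reverses the verdict. It does so only with a one-sided rule and with children who have validated TB kept as TB-free. At the planned 15% missed (about 27 of 176, lower bound 79.5%) the algorithm passes without any relabelling.

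Three further points have weight.
- The Introduction expects the IRIS risk to be low, so the larger shares in the table are there for range, not as forecasts. It would also be tempting to say that about 88 of the 176 could be so labelled because half are expected to be on ART. That assumes the 50% applies to algorithm-negative children, which the protocol does not state.
- The Introduction does not say that every case labelled potential unmasking IRIS was TB at the baseline decision. ART may start later: in the earlier study the median was 14 days in children not treated for TB. Treating such cases as baseline misses is a reasonable inference, not a quoted rule.
- The adjudicators are independent of study management (Section 13.5). That guards against motivated labelling but does not settle which classes count.

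Finally, a reader might extend the argument to new infections. It does not reach them: a new infection after baseline is not a baseline false negative, and keeping it apart fits the endpoint.

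**Conclusion.** The point holds as an internal conflict over the primary numerator. Sections 3.3 and 11.2.1 together allow a reading in which IRIS-labelled cases are not counted; the Introduction ties those cases to missed TB; Sections 4.2, 4.3 and 13.3 count them. The reading that leaves them out biases the NPV upward and raises the false-validation risk above the planned level.

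The size cannot be fixed from the protocol. The figures of 18% or 12% at a 10% share, and 45% or 29% at a 20% share, rest on four assumptions: a true NPV of exactly 75%, 176 evaluable children, the exact one-sided 5% rule, and the assumed IRIS share. This is a conflict between stated rules, not a detail left for the statistical analysis plan, because the protocol itself fixes the endpoint, the formula, the limit and the committee's classes.

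**What to change.** - Reconcile Sections 3.1, 3.3, 4.2 and 11.2.1 by stating that validated TB labelled unmasking IRIS, in a child not treated as per the algorithm, counts as a missed (false negative) case in the primary NPV.
- Report the Expert Committee's IRIS classification descriptively.
- New infections may remain a separate class. State the criteria for that class, and whether these children stay in the denominator.
- Add a sensitivity analysis counting all incident TB over 6 months, which is the quantity used in Section 4.3 and reported to the IDMC under Section 13.3.

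Cost: a wording amendment and one extra analysis. The reported NPV may be slightly less favourable. The design is unchanged: 176 children, at most 34 misses, α 4.6%, power 95.2%.

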4. STUDY DESIGN

4.1. Study type

TB-Speed HIV is a prospective multicentre management study evaluating the safety and feasibility of the recently proposed PAANTHER TB treatment decision algorithm for HIV-infected children with presumptive TB. It will be conducted in four countries with high and very high TB incidence (Côte d'Ivoire, Uganda, Mozambique, and Zambia) which have not participated in the study that developed the PAANTHER algorithm.

4.2. Methodology

The PAANTHER algorithm was initially developed in two countries from South-East Asia (Cambodia, Vietnam) and two West African countries (Burkina Faso, Cameroon). To assess the algorithm's performance outside of its development settings, the study will be purposefully implemented in 4 different countries across Africa where TB incidence, HIV prevalence, patient mix and healthcare practices are likely to vary: Côte d'Ivoire, Uganda, Mozambique, and Zambia (Table 1).

The PAANTHER TB treatment decision algorithm will be used for a TB treatment decision by site clinicians in all children enrolled in the study. Validation of the algorithm will be performed by evaluating the proportion of missed TB cases in children not initiated on treatment as per the PAANTHER TB treatment decision algorithm. The safety of this strategy will be carefully assessed through review of safety reports every 4 to 6 months during study conduct by the IDMC.

Occurrence of algorithm failures in terms of missed TB cases (TB cases subsequently detected among untreated cases, i.e. false negatives) and cases with unlikely TB among those initiated on TB treatment as per the algorithm (cases not secondarily validated as confirmed or unconfirmed TB cases by the Expert Committee, i.e. false positives) will enable to estimate the negative and positive predictive values of the algorithm.

A centralized international Expert Committee will clinically review and validate TB diagnosis in children. This will enable assessment of the added value of new markers (MLR and CRP) and, if need be, to propose a new version of the score based on an optimised predicted probability.

• Study adaptation to the Covid-19 pandemic

All enrolments in the TB-Speed HIV study have been stopped as of April 1st, 2020 due to the Covid-19 outbreak. This was justified by the complete or partial lock down in project countries, the lack of protective equipment to ensure safety of participants and study staff, and the difficulty to conduct proper study monitoring. The decision was approved by the TB-Speed SAB. All study sites were instructed: 1) to suspend all enrolments until further notice; 2) to conduct phone-based follow-up when physical visits are not possible, provided the participant's safety is not compromised, based on ad hoc SOPs for remote follow-up; 3) to limit face-to-face contact to that strictly necessary to provide care that cannot be suspended, provided the safety of staff is protected, based on ad hoc SOPs for infection prevention and control (IPC) during health care, samples collection and samples processing at the laboratory.

Enrolments resumed progressively at sites from June 2021, depending on country situations and appropriate safety measures (see section 7.14). However, the arrangements described above may be reapplied if the epidemiological context and government restrictions require so. These also include remote site monitoring (see section 16.2.3).

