7.12.2. Loss to follow-up

When a child for whom parent(s)/guardian(s) have not explicitly withdrawn consent does not show up for routine clinic visits, the trial team must make every effort to contact him/her. With their prior agreement, the trial team will contact the parent(s)/guardian(s) via telephone or any other means available and acceptable locally (home visits, home base care team). The investigator should show "due diligence" by documenting in the source documents steps taken to contact the patient.

A child who has not withdrawn consent or transferred out, and who does not show up at the M6 visit is considered definitely lost to follow-up in the trial, unless he/she is known to be deceased. The date of lost to follow-up will be the date of his/her last contact with the trial team (either at the hospital, via telephone, or at home).

A particular attention will be given to the descriptive analysis of patients lost to follow-up and protocol withdrawals during the study: numbers, characteristics and reasons for refusal/lost to follow-up.

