11.2.3. Analysis of secondary endpoints

The median time to TB treatment decision and interquartile range, and the proportion of children with presumptive TB having completed the PAANTHER TB treatment decision algorithm will be estimated.

We will assess the proportion of HIV-infected children with unlikely TB among those initiated on treatment as per the PAANTHER TB treatment decision algorithm (false positive cases) identified by the international Expert Committee. We will estimate the positive predictive value (PPV) and its 95% confidence intervall. Once PPV and NPV are assessed, we will estimate sensitivity and specificity of the algorithm/scoring system and TB prevalence.

Discrimination and calibration, which are key measures of a model's predictive performance, will be quantified for the original model and the model incorporating new predictors. To avoid adding optimism, the original model will not be redeveloped. Discrimination of the model, measured by the C statistic, or area under the receiver operating characteristic (AUROC) curve, will be estimated for the original model and parameters with and without potential new predictors such as MLR and CRP. AUCs of the models will be compared using bootstrapping technique. Calibration examines the agreement between predicted and observed risk of disease and can be quantified by a calibration slope and the expected/observed (E/O) statistic (ratio of the total expected to have disease to the total observed with disease). TB diagnosis as assessed through the Expert Committee review of false negative and false positive cases will be used as reference standard.

Sensitivity analyses will be conducted to assess impact of age, ART, CD4, and nutritional status on the performance of the score. Furthermore, the score will be assessed country-wise to identify potential heterogeneity in score performances between countries.

If a lower predictive accuracy is found, we will update the existing prediction model and adjust or recalibrate it to the validation sample. As a result, the updated model combining the information from the original PAANTHER model with new information from the TB-Speed study, will probably have improved transportability to other populations.

Sensitivity, specificity, and predictive values of Ultra in NPA and stool will be measured for each specimen independently and for the combination of the 2 specimens against mycobacterial culture.

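### An untreated child who dies without a TB diagnosis has no stated route to a TB verdict, so the primary NPV can be too high by an amount the protocol does not bound

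*Protocol*

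**What the plan says.** Section 4.2 describes failures on the untreated side as "missed TB cases (TB cases subsequently detected among untreated cases, i.e. false negatives". Section 4.3 measures them by incident TB in the six months after the algorithm is applied. Section 11.2.1 sets NPV at one minus the false-negative proportion and compares it with 75%.

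The review pathway has the same boundary. In section 3.3 the national committee is to "review and validate all new TB cases in children initially non-treated for TB". The international Expert Committee then decides "whether missed TB cases are false negatives, potential TB unmasking IRIS or new TB infections". Section 11.2.3 states: "TB diagnosis as assessed through the Expert Committee review of false negative and false positive cases will be used as reference standard".

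Deaths and losses are handled elsewhere:
- Mortality at six months is a secondary endpoint (section 3.2). It also goes to the IDMC alongside the missed cases (sections 11.2.2 and 13.3).
- For losses, section 7.12.2 says: "A particular attention will be given to the descriptive analysis of patients lost to follow-up".
- The sample size in section 4.3 is set "taking into account an expected 10% of missing data".

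No section shown says how an untreated child who dies or is lost without a TB diagnosis enters the primary proportion.

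**The concern.** The study's main claim is that withholding TB treatment on a negative algorithm result is safe. The most serious failure is a child with TB who is left untreated and dies before TB is recognised. Under the definition as written, that child is not a detected case and so does not enter the numerator. Whether the child stays in the denominator as a non-case or leaves the analysis is not stated.

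The introduction makes such deaths foreseeable. It attributes one-third of deaths in HIV-infected children to TB, and it says untreated TB raises the risk of death. Of 266 ART-naïve children in the development study it reports that "26 and 24 deaths occurred before and after ART initiation, respectively". Any error from unrecognised TB deaths counted as non-cases favours validation. The 10% allowance for missing data protects precision and does nothing against this bias.

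**Working it through.** **1. The plan's own figures.** Inputs from section 4.3: sensitivity 89%, specificity 61%, prevalence 50%, NPV 85% expected and 75% unacceptable, one-sided 5%, β = 5%, 10% missing.
- Score-negative share = 0.5 × 0.11 + 0.5 × 0.61 = 0.36.
- Miss proportion = 0.055 / 0.36 = 15.3%.
- The exact binomial test of 75% against 85% needs n = 176 (validate at 142 or more TB-free; level 4.6%, power 95.2%). This equals the stated 176.
- Total = 176 / 0.36 / 0.90 = 544 after rounding up, close to the stated 550.

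The planning arithmetic is sound.

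**2. The pass mark.** 550 × 0.36 = 198 score-negative children. At n = 198 the exact one-sided 5% rule needs 159 or more TB-free, so it allows at most 39 misses (level 4.8%).

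**3. Bias in the estimate.** Let U of N children be unresolved, with TB fraction q, and let the miss rate among the rest be 15%.
- Counted as non-cases: NPV is overstated by (U/N) × q.
- Dropped: NPV is overstated by (U/N) × (q − 0.15).

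With N = 198 and U = 20 (both assumptions):

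| q among the 20 | True NPV | Non-case reading | Excess, points | Dropped | Excess, points |
|---|---|---|---|---|---|
| 15% | 85.0% | 86.5% | 1.5 | 85.0% | 0 |
| 1/3 | 83.1% | 86.5% | 3.4 | 85.0% | 1.9 |
| 50% | 81.5% | 86.5% | 5.1 | 85.0% | 3.5 |
| 100% | 76.4% | 86.5% | 10.1 | 85.0% | 8.6 |

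**4. False validation when the true NPV is exactly 75%.** Same N and U, with q = 1/3. The TB-free share among the 178 resolved children is (0.75 × 198 − 20 × 2/3) / 178 = 135.17 / 178 = 0.759.
- Non-case reading: the 20 count as TB-free, so 139 or more of 178 are needed. Probability about 28%.
- Dropped: the exact rule at n = 178 needs 144 or more. Probability about 7%.

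**5. When would a passing result reverse?** Failure needs 40 or more misses in 198.
- If 30 misses are already detected (15% of all 198), 10 more reverse it. That is half of 20 unresolved children, or one-third of 30.
- If the 15% applies only to resolved children, 20 unresolved leave about 27 detected misses (0.15 × 178 = 26.7), and 13 of the 20 would need to have TB. With 30 unresolved there are about 25 detected misses (0.15 × 168 = 25.2), and 15 of the 30 would need to have TB.

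**The case against.** The protocol has real safeguards:
- Culture on two gastric aspirates or sputa is planned for every child. A positive result returned after death could still count as detected TB.
- Untreated children have six scheduled visits, CXR at M2 and M6, and repeat sampling if they do not improve. Lost children are traced.
- The national committee validates adverse-event diagnoses, deaths are notified to the sponsor, and the Expert Committee has a general remit to validate final TB diagnosis.
- Handling of missing outcomes is normal SAP content, and the flow chart is not visible in the text reviewed.

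These points narrow the concern but do not remove it. The introduction itself calls culture inadequately sensitive, and a child who has died has no later CXR. No section turns adverse-event validation or IDMC reporting into a TB verdict that feeds the primary proportion. The definition of a miss and the limits of the reference standard are stated in the protocol, so this is not simply a matter left to the SAP.

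A reader might infer more: that the protocol counts these deaths as successes, that NPV is certainly inflated, or that 18.8% (50/266) of untreated children will die. The documents do not support this. No classification rule is written down. Under exclusion, upward bias needs TB to be more frequent among the unresolved than the roughly 15% in the rest, and no TB rate is given for lost children. The 18.8% covers ART-naïve children only and pools TB-treated with untreated, whereas this study expects half to be on ART and lets clinicians treat severely ill children who score below 100.

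**Conclusion.** The point stands as a gap in a stated rule. Applied literally, the endpoint and its review pathway give an untreated child who dies undiagnosed no TB verdict. The direction of bias is upward under the non-case reading if any such child had TB. Under exclusion it depends on the TB fraction.

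The size is not fixed by the documents. The 28% and 7% figures rest on 198 score-negative children, 20 unresolved, one-third of them with TB, and the one-sided 5% test of section 4.3. The one-third is the introduction's figure for deaths in HIV-infected children generally and was not measured in score-negative children.

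Plausible numbers erode the margin to 39 misses. They reverse a passing result only when the unresolved share and its TB fraction are both high. The change is worth making before outcomes are known, because a rule chosen afterwards could decide validation.

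**What to change.** In sections 3.3 and 11.2.1:
- Send every death in an untreated child to the Expert Committee for a verdict of TB, not TB or indeterminate, using baseline culture, Ultra, CXR and clinical data.
- Count TB-adjudicated deaths as missed cases in the primary analysis.
- Report NPV with indeterminate deaths counted as missed and again as not missed. Counting all of them as missed in the primary analysis would push NPV towards a TB-or-death composite, so that belongs in a sensitivity analysis.
- For children lost or withdrawn before M6, add a tipping-point analysis: the TB fraction among them at which the lower bound falls to 75%.

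The cost is a limited number of extra dossiers for an existing committee, one sensitivity analysis, and a slightly less favourable NPV.
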